13.2 Serious Adverse Events

An SAE is defined as an AE that results in any of the following:

- Death
- Life-threatening (at the time of the event)
- Requires inpatient hospitalization or prolongs existing inpatient hospitalization
- Results in persistent or significant disability or incapacity
- Results in a congenital abnormality or birth defect
- An important medical event that requires medical intervention to prevent any of the above outcomes

Important medical events are those that may not be immediately life-threatening, but may jeopardize the patient and may require intervention to prevent one of the other serious outcomes listed above. Examples of such events are intensive treatment in an emergency room or at home for allergic bronchospasm, blood dyscrasias or convulsions that do not result in hospitalization.

Inpatient hospitalization or prolongation of existing hospitalization means that hospital inpatient admission and/or prolongation of hospital stay were required for treatment of AE, or that they occurred as a consequence of the event. It does not refer to pre-planned elective hospital admission for treatment of a pre-existing condition that has not significantly worsened, or to diagnostic procedure.

The term “life-threatening” in the definition of “serious” refers to an event in which the patient was at risk of death at the time of the event; it does not refer to an event that hypothetically might have caused death if it were more severe.

Any new SAE that occurs during the study period should be recorded and reported immediately (See Section 8.11) if it occurred after the patient has signed the ICF and within 30 days of the last study treatment dose of each course. Serious and non-serious adverse events occurring after the study-specific informed consent is signed but prior to Study Day 1 will be collected only if they are considered by the investigator to be causally related to the study-required procedures.

13.3 Study-Specific Exceptions

Cytopenias (anemia, neutropenia, or thrombocytopenia) are part of the natural history of MDS and AML. Persistent cytopenia at the same CTCAE grade as at baseline are not to be reported as adverse events, unless the investigator had an identifiable cause other than the underlying disease.

Events that are clearly consistent with the expected pattern of progression of the underlying disease are also considered an expected outcome for this study and will not be subject to expedited reporting.

Serious and nonserious adverse events occurring after the study-specific informed consent is signed but prior to the initial dose of study drug will be collected only if they are considered by the investigator to be causally related to the study-required procedures.

13.4 Assessment of Causality

The causal relationship between an AE and study treatment will be determined and documented by the responsible Investigator or designee, according to best medical judgment, as presented in table below.

Adverse Event Relationship Criteria

Term	Definition	Clarification
No Reasonable Possibility	This category applies to those AEs which, after careful consideration, are clearly due to extraneous causes (disease, environment, etc.) or to those AEs, which after careful medical consideration at the time they are evaluated, are judged to be unrelated to study treatment	An adverse experience may be considered “No Reasonable Possibility” if it is clearly due to extraneous causes or when (at least 2 of the following): 
• It does not follow a reasonable temporal sequence from the administration of study treatment• It could readily have been produced by the patient’s clinical state, environmental or toxic factors, or other modes of therapy administered to the patient

		
 • It does not follow a known pattern of response to study treatment • It does not reappear or worsen when the study treatment is re-administered

Reasonable Possibility
	
This category applies to those AEs for which, after careful medical consideration at the time they are evaluated, a connection with STUDY TREATMENT administration cannot be ruled out with certainty or which are felt with a high degree of certainty to be related to study treatment.
	
An adverse experience may be considered “Reasonable Possibility” if or when (at least 2 of the following):
 
 • It follows a reasonable temporal sequence from administration of study treatment • It could not be reasonably explained by the known characteristics of the patient’s clinical state, environmental or toxic factors, or other modes of therapy administered to the patient • It disappears or decreases on cessation or reduction in dose. There are important exceptions when an adverse event does not disappear upon discontinuation of the drug, yet drug-relatedness clearly exists • It follows a known pattern of response to study treatment

13.5 Suspected Unexpected Serious Adverse Reaction (SUSAR)

A SUSAR is a Suspected Unexpected Serious Adverse Reaction. An Adverse Reaction is defined as any AE caused by a drug. A suspected Adverse Reaction is defined as an AE for which there is a reasonable possibility that the drug caused the AE. The "reasonable possibility" means that there is evidence to suggest a causal relationship between the drug and the AE. Unexpected Adverse Reaction means a reaction which is not included in the Adverse Reaction section of the relevant Reference Safety Information by its specificity, severity, outcome or frequency. The relevant Reference Safety Information of this study is provided in the study treatment IB.

13.6 Reporting of AE/SAE that occur before treatment

For this trial, the only adverse events that will be counted will be treatment-emergent events. These events are those that started after the start of the treatment period, or were present prior to the start of the treatment period but increased in severity, changed from being not suspected to being suspected to be due to study drug, or developed into an SAE after the start of the treatment period.

Each AE will be counted once according to the date of onset. If the AE onset was prior to the first dose of study drug and the event does not increase in severity after initiation of study drug, the AE is then considered to be a pretreatment adverse event and will not be counted in the treatment emergent adverse event incidence tables. If the onset is prior to the first dose of study drug and the severity increases thereafter, the event is counted as a treatment emergent AE. An AE with onset after the first dose of study drug will be counted as a treatment emergent AE. This rule is consistent with the treatment emergent signs and symptoms convention for counting AEs.

All AEs (ie, pretreatment AE and treatment emergent AEs) will be reported separately. All AEs will be split between pretreatment and post treatment phases.

13.7 Recommendations related to contraception and pregnancy

Subjects with reproductive potential are defined as sexually mature women who have not undergone a hysterectomy, bilateral oophorectomy or tubal occlusion or who have not been naturally postmenopausal (i.e., who have not menstruated at all) for at least 24 consecutive months (i.e., has had menses at any time in the preceding 24 consecutive months).

If of childbearing potential (males and females), willing to use an effective form of contraception such as latex condom, hormonal birth control, intrauterine device or double barrier method during chemotherapy treatment and for at least three months thereafter.

Pregnant women are excluded from this study. Because there is an unknown but potential risk for adverse events in nursing infants secondary to treatment of the mother with venetoclax, breastfeeding should be discontinued if the mother is treated with venetoclax.

Contact information for Safety reporting

Sponsors contact department:

[name]
Directrice du GFM
Hôpital Saint Louis
Service Hématologie Séniors
[name]
[name]
Phone : [name]
Fax : [name]
Email : [contact]

Each SAE and pregnancy must be followed up until resolution or stabilization by submission of updated reports (FU-report) to the designated recipient.

The sponsor will inform AbbVie about all serious adverse events, SUSARs and all suspected pregnancies within 24 hours of their knowledge of the event. Reports to AbbVie must be submitted via email to [contact]

The sponsor will also provide to AbbVie

- A listing of non-serious AEs, if requested
- Final study report

13.8 Investigator reporting responsibilities

Any fatal or life-threatening event should be reported immediately to GFM. These preliminary reports will be followed within 24 hours by detailed descriptions that include a completed SAE form, copies of hospital case reports, autopsy reports and other documents, when requested and applicable.

The investigator must complete the SAE Report Form in English, assess the relationship to study treatment and submit it via fax or email within 24 hours to GFM listed above.

Follow-up information is to be submitted on a new SAE form. The new form should clearly state that it is a follow-up to the previously-reported SAE and give the date of the original report. The follow-up SAE report should describe whether the event has resolved or continues, if and how it was treated and whether the patient continued or discontinued study participation.

The following information should be provided in the SAE form to accurately and completely record the event:

1. Investigator name and site address
2. Patient study identification number
3. Patient demographics (gender, year of birth or age, weight, height)
4. Clinical Event:

- Description
- Date and time of onset, stop date, or duration
- Severity
- Treatment (including hospitalization)
- Relationship to study treatment (causality)
- Action(s) taken regarding study treatment
- Information on recovery and any sequelae
- If the SAE resulted in death, cause of death (whether or not the death was related to study treatment)
- Autopsy findings (if available)
- Medical History case report form (copy)
- Concomitant Medication case report form (copy)
- Any relevant reports (laboratory, discharge, etc.)

Accompanying documentation, such as copies of hospital case reports, autopsy reports and other documents when applicable, should be summarized on the SAE form and a copy of the source document may be sent if required. The patient's personal details will be removed and replaced with study identifiers i.e. study number and initials, if applicable.

In addition, all AEs / SAEs / SUSARs will be reported to the ethics committee (EC/IRB) and regulatory authorities as required by local regulations and International Conference on Harmonization (ICH)-GCP guidelines.

Minimal information should include:

- An identifiable patient (e.g., patient study code number)
- An identifiable reporting sources
- All related AEs

Follow-up of SAEs / SUSARs

Follow-up of SAEs / SUSARs that occur during the study will continue until their satisfactory resolution or stabilization.

If supplementary information becomes available, a follow-up SAE Report Form must be completed by the site and faxed or emailed within 24 hours to GFM.

The contact information for follow-up SAE reporting is the same as for initial SAE reports (as detailed in the section above).

Once faxed or emailed, the SAE form and accompanying documentation should be placed in the SAE section of the Investigator's file. If supplementary information on a SAE has to be sent, the SAE form to be used must be marked as "follow-up report".

13.9 Sponsors reporting responsibilities

For all SAEs the sponsor has to carry out a separate assessment for expectedness, seriousness and causal relationship to treatment with the study medication.

Every SUSAR that becomes known in a clinical trial will be reported by the sponsor to the competent authority and the Ethics Committee.

The sponsor will inform all investigational sites about reported relevant events (e.g. SUSARs) according to all applicable regulations.

The sponsor will inform AbbVie about all serious adverse events, SUSARs and all suspected pregnancies within 24 hours of their knowledge of the event, as outlined in section 13.7.

13.10 Notification of SAEs to the Ethics Committee

Notification of the IECs / IRBs about all relevant events (e.g. SAEs, suspected, unexpected, serious adverse reactions (SUSARs)) will be performed by the sponsor according to all applicable regulations.

13.11 Contact information of the competent authority

The processing and reporting of all relevant events (e.g. SAEs, SUSARs) to the authorities will be done by the sponsor according to all applicable regulations.

13.12 Annual safety report (DSUR) of trial subjects

Once a year or on demand, the sponsor will supply a report on the safety of trial subjects with all relevant information during the reference period to the competent authority and the ethics committee.

The reference period for the annual report on the safety of trial subjects begins with the date that the trial is approved by competent authority. This date is the reference date for the start of the year of the annual safety report. The sponsor will supply the report within 60 days of one year after the reference date.

13.13 PREMATURE TREATMENT DISCONTINUATION (Discontinuation of Individual Subjects)

Treatment will continue until the occurrence of any of the following events:

- No response after 8 cycles of therapy
- Major violation of the study protocol (violations that affect the right and safety of patients and the integrity of collected data)

- Unacceptable AE or failure to tolerate study therapy
- All grade 4 toxicities
- Persistent myelosuppression and/or cardiac toxicity
- Disease progression
- Withdrawal of consent
- Lost to follow up
- Death
- Suspected pregnancy
- Administrative decision by the investigator or the sponsor
- If the patient manifests exclusion criteria during the trial
- Subject noncompliance (deliberate protocol violations)
- A subject requires the use of a proscribed medication; the subject will need to be discontinued from treatment and end of treatment and end of study visits performed.

Where possible, patients who have discontinued their treatment prematurely will receive the same follow-up as other patients.

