6 INVESTIGATIONAL PLAN

6.1 Overall design

This is an open label multicenter phase I/II study. Patients will be treated with venetoclax during 14 days in combination with AZA at 75 mg/m²/day for 5 days for each cycle or 50 mg/m²/day for 5 days each cycle if relapse occurred less than 4 months after allo SCT.

Patients who meet eligibility criteria will be administered VENETOCLAX orally at starting dose in phase I part and at MTD in phase II part on days 1-14 in combination with AZA at 75 mg/m²/day for 5 days on days 1-5 for each cycle or 50 mg/m²/day for 5 days each cycle if relapse occurred less than 4 months after allo SCT.

Following cycles must be administered on day 28 or delayed until day 42 in cases of hematological toxicity. Each cycle will last 28 days starting on day 1 of each cycle when ANC > 1 G/L and platelet > 50 G/L without transfusion or when recovery of baseline level.

In the phase I part, VENETOCLAX will be given once daily orally on days 1-14 for all cycles at escalating doses starting at Dose Level 1 (defined below) in combination with AZA +/- DLI. Patients will receive at least 8 cycles of VENETOCLAX/AZA/DLI unless progression occurs. Response will be assessed after 4, 6 and 8 cycles. Patients achieving a response (see appendix 11 and 12) will be able to continue on protocol with VENETOCLAX + AZA until 12 cycles maximum then with AZA alone. In the absence of response, patients will stop treatment.

Dose Levels for Treatment in Phase I

Dose Level	VENETOCLAX (mg)	Azacitidine (mg/m ²)
-1	50 mg*	75 (50 if relapse < 4 months)
1 (Starting dose)	100 mg*	75 (50 if relapse < 4 months)
2	200 mg*	75 (50 if relapse < 4 months)
3	400 mg*	75 (50 if relapse < 4 months)

*VENETOCLAX will be given once daily orally during 14 days.

In the phase II part, VENETOCLAX will be given once daily orally on days 1-14 for all cycles at MTD defined in the phase I part of the study in combination with AZA/DLI. Patients will receive at least 8 cycles of VENETOCLAX/AZA/DLI unless progression occurs. Response will be assessed after 4, 6 and 8 cycles. Patients achieving a response (defined below) will be able to continue on protocol with VENETOCLAX + AZA until 12 cycles maximum then AZA alone. In the absence of response, patients will stop treatment.

Ramp-up** will be performed at the beginning of cycle 1:

Dose Level	VENETOCLAX D1C1	VENETOCLAX D2C1	VENETOCLAX D3C1 and beyond
-1	10 mg*	20 mg*	50 mg*
1 (Starting dose)	20 mg*	50 mg*	100 mg*
2	50 mg*	100 mg*	200 mg*

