13.17 Study Stopping Rules

Study Stopping Rules in the phase I

The dose limiting toxicities (DLT) observation period is defined as the first treatment cycle (Cycle 1) of venetoclax combined with azacitidine.

Dose limiting toxicities for dose escalation purposes will be determined based on adverse events that occur during the DLT observation period.

Adverse events occurring after the DLT observation period criteria will also be reviewed and may be taken into consideration for dose escalation decisions.

Any of the following events will be considered a DLT unless the event can be attributed by the investigator to a clearly identifiable cause such as underlying illness or disease progression, concurrent other illness, or concomitant medication:

- ANC $< 1 \times 10^9/L$ (Grade ≥ 3) which does not recover as defined below:
 - o Recovery is defined as an increase in ANC from nadir by $\geq 50\%$ of the reduction from baseline to nadir or any increase to an ANC of $\geq 1 \times 10^9/L$ within 42 days from Day 1 of Cycle 1
 - o Delayed recovery should only be deemed a DLT if due to treatment induced toxicity as confirmed by a bone marrow sample showing an overall bone marrow cellularity of $< 5\%$
- Grade ≥ 3 thrombocytopenia associated with clinically significant bleeding that requires transfusion of platelets over routine or baseline transfusion needs based on investigator opinion
- Grade ≥ 4 non-hematologic toxicity deemed related to venetoclax per investigator opinion.
- Grade 4 infections or complications related to infections (e.g., sepsis) should only be deemed DLTs if due to treatment-induced neutropenia as confirmed by a bone marrow sample showing an overall bone marrow cellularity of $< 5\%$

Occurrence of a DLT event will require an interruption and possible discontinuation of study treatment administration to the patient that experienced the DLT. All decisions regarding continued dosing for individual subjects will be medically managed by the investigator, per discussion with the GFM, as appropriate. These decisions will be driven by the definition of DLTs as described above.

In addition, any treatment related death will be reported to the safety committee within 24 hours, the safety committee will review, discuss and provide guidance to the sponsor according to the safety committee charter.

Study Stopping Rules in the phase II

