Any of the following events will be considered a DLT unless the event can be attributed by the investigator to a clearly identifiable cause such as underlying illness or disease progression, concurrent other illness, or concomitant medication:

- ANC $< 1 \times 10^9/L$ (Grade ≥ 3) which does not recover as defined below:

- Recovery is defined an increase in ANC from nadir by $\geq 50\%$ of the reduction from baseline to nadir or any increase to an ANC of $\geq 1 \times 10^9/L$ within 42 days from Day 1 of Cycle 1
- Delayed recovery should only be deemed a DLT if due to treatment induced toxicity as confirmed by a bone marrow sample showing an overall bone marrow cellularity of $< 5\%$
- Grade ≥ 3 thrombocytopenia associated with clinically significant bleeding that requires transfusion of platelets over routine or baseline transfusion needs based on investigator opinion
- Grade ≥ 4 non-hematologic toxicity deemed related to venetoclax per investigator opinion.
- Grade 4 infections or complications related to infections (e.g., sepsis) should only be deemed DLTs if due to treatment-induced neutropenia as confirmed by a bone marrow sample showing an overall bone marrow cellularity of $< 5\%$

We will stop the enrollment of new patients at the request of the DSMB if DLT attributable to VEN > 2 . Ongoing patients without toxicities and with a benefit of treatment at the investigator's discretion will be allowed to continue to receive treatment according to the protocol.

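### Section 13.13 ends treatment for every grade 4 toxicity, which conflicts with the protocol's own rule for recovering cytopenia and, for one class of phase I DLT, with section 13.17

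*Protocol*

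**What the plan says.** Section 13.13 (premature treatment discontinuation of individual subjects) opens by saying that treatment goes on until any one of the listed events occurs. One entry is "All grade 4 toxicities". The entry before it covers unacceptable adverse events or failure to tolerate therapy. The entry after it covers persistent myelosuppression and cardiac toxicity.

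Four other rules bear on the same patients:

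- **6.1, both phases:** "Following cycles must be administered on day 28 or delayed until day 42 in cases of hematological toxicity". A cycle restarts when ANC is above 1 G/L and platelets are above 50 G/L without transfusion, or when counts are back at baseline. No toxicity grade limits this rule.
- **6.5:** G-CSF may be given for grade 3 to 4 neutropenia.
- **13.17, DLT definition, the same in both phases:** low neutrophils count only if they fail to recover "within 42 days from Day 1 of Cycle 1" and marrow cellularity is below 5%. For platelets, the DLT is grade 3 or higher "thrombocytopenia associated with clinically significant bleeding that requires transfusion of platelets over routine or baseline transfusion needs". Outside the blood counts, it is grade 4 or higher "non-hematologic toxicity deemed related to venetoclax per investigator opinion".
- **13.17, phase I only, what follows a DLT:** "Occurrence of a DLT event will require an interruption and possible discontinuation of study treatment administration". It adds: "All decisions regarding continued dosing for individual subjects will be medically managed by the investigator", in discussion with the sponsor group.

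**The concern.** The grade 4 entry carries no qualifier, the list is mandatory, and no clause says which section prevails. A site that follows 13.13 to the letter takes a patient off venetoclax and azacitidine for a grade 4 neutropenia that recovers in time for the next cycle. A site that follows 6.1 waits and resumes. In phase I, two sites could likewise handle the same related grade 4 non-haematological DLT differently, one under 13.13 and the other under 13.17.

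What is at stake is consistent conduct across roughly 20 sites, and treatment for patients whose toxicity the protocol elsewhere regards as manageable. Treatment exposure, and with it the chance to respond, would depend partly on which section a site happened to follow.

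**Working it through.** No stated figure is in dispute, so the check sets the rules side by side for each kind of event.

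| Event | 13.13 read literally | Other sections | Result |
|---|---|---|---|
| Treatment-induced grade 4 neutropenia, recovers by day 42 | Treatment ends | 6.1: delay, then restart. 6.5: G-CSF allowed. 13.17: not a DLT | Conflict, both phases |
| Grade 4 thrombocytopenia, no significant bleeding, recovers by day 42 | Treatment ends | 6.1: delay, then restart. 13.17: not a DLT | Conflict, both phases |
| Cytopenia not recovered by day 42 | Ends, if grade 4 or if it counts as persistent myelosuppression | 6.1: delay allowance used up | Compatible |
| Grade 3 DLT, phase I | Not covered by the grade 4 bullet | 13.17: interrupt, possibly discontinue | Compatible |
| Venetoclax-related, non-fatal grade 4 non-haematological DLT, phase I | Treatment ends | 13.17: interrupt, possibly discontinue, investigator manages | Conflict, phase I |
| The same event, phase II | Treatment ends | 13.17, phase II: no rule on dosing after a DLT | No conflict |

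**Strength of each comparison for cytopenia.** Section 6.1 is the direct conflict, because it says what happens to the next cycle and applies to every cycle. The DLT definition is supporting evidence: its recovery window is tied to Cycle 1, and it classifies events without saying who stays on treatment. Section 6.5 is weaker still, since permission to give G-CSF does not itself promise further study drug.

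**The neighbouring bullet.** If every grade 4 cytopenia already ended treatment, the persistent-myelosuppression entry would add nothing for grade 4 counts. It would still serve for lasting grade 3 cytopenia. So the list itself hints that its authors had transient cytopenia outside the grade 4 bullet, but the text does not say so.

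**Do 13.1 or 13.3 provide the missing exception?** No. Section 13.1 keeps disease-related laboratory values within the expected course out of AE classification, and 13.3 keeps persistent cytopenia at the baseline grade out of AE reporting. Neither says when treatment ends, and neither covers a new cytopenia caused by treatment.

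**Why the second conflict is confined to phase I.** The sentences on dosing after a DLT stand only under the phase I heading. The phase II part sets an enrolment rule, "We will stop the enrollment of new patients at the request of the DSMB if DLT attributable to VEN" exceeds two, and lets ongoing patients without toxicities continue. It gives no instruction for the patient who had the DLT, so it does not contradict 13.13.

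**The case against.** The best reply is that the list should be read as a whole. The entry on persistent myelosuppression deals with blood counts, the grade 4 entry naturally covers the rest, and that reading agrees with 6.1 and 6.5. The reply has real force: it makes this a drafting fault and not a deliberate policy of stopping for transient cytopenia. It does not remove the point, because the word used is all, and a site is not bound to choose the milder reading.

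For phase I, the 13.17 sentence has to cover grade 3 DLTs as well, so making discontinuation only possible is correct as a general statement, and 13.13 could be read as saying which DLTs go on to discontinuation. That stands, and it leaves just one class in dispute. It can also be said that a strict stop after allogeneic transplantation is a legitimate safety choice. For non-haematological grade 4 events that is accepted, and the fix keeps it.

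Two further sections might be cited, but they prove little. Section 6.3 asks for TLS risk to be reassessed after an interruption of more than two weeks. It does not say that a patient with a grade 4 toxicity resumes. Section 6.6 sets no minimum ANC or platelet count, but low counts at entry are not a treatment toxicity.

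**Conclusion.** The point holds in a limited form. Taken literally, the grade 4 bullet in 13.13 contradicts 6.1 for recovering, treatment-induced grade 4 cytopenia in both phases. It also contradicts 13.17 for venetoclax-related, non-fatal grade 4 non-haematological DLTs in phase I. That the stop is permanent is an inference from the section heading, from the lead-in, and from the absence of any restart provision in 13.13; the section does not use the word. The weight is minor.

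Three stronger conclusions are tempting, and the protocol does not support them.

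- **A count of patients affected.** Section 2 reports grade 4 platelet decrease in 30% and grade 4 neutrophil decrease in 20% of ten patients, and a reader might scale this up to the 30 phase II patients. The series is too small (exact 95% intervals 7 to 65% for 3/10 and 3 to 56% for 2/10). It used 400 and 800 mg, whereas this trial starts at 100 mg and goes no higher than 400 mg, for 14 days per cycle, after transplantation. Neither timing nor overlap is given, nor how many of the events recovered.
- **A loss of power.** This would need an assumed share of patients stopped before the assessment after cycle 4, all counted as non-responders. Appendix 1 requires a marrow aspirate at premature termination, and 13.13 asks for the same follow-up where possible, so a stopped patient is not automatically a non-responder.
- **A contradiction with 13.17 in phase II.** There is none, because the phase II part gives no rule on individual dosing.

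**What to change.** In 13.13, change the bullet to *All grade 4 non-haematological toxicities*. Leave cytopenia to three rules that already exist: the 6.1 delay, the persistent-myelosuppression bullet and the unacceptable-AE bullet. Define persistent myelosuppression as failure to meet the 6.1 restart condition by day 42. Using the 6.1 condition for continuation keeps it apart from the DLT recovery rule in 13.17, which also accepts regaining half of the fall in ANC.

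In 13.17, state that grade 4 non-haematological DLTs end treatment under 13.13. State also that thrombocytopenia with clinically significant bleeding is treated no more leniently than cytopenia that is not a DLT. Without that second sentence, the bleeding case would face only possible discontinuation while a milder, non-bleeding cytopenia faced a firm day-42 limit. The clinical team should confirm the wording.

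The cost is a small protocol amendment, with ethics committee and authority approval where section 22 requires it. Some patients with recovering grade 4 cytopenia will stay on treatment longer, and the unacceptable-AE bullet remains as a safeguard for them. The sample size and the two-stage decision rule do not change.
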